11.4.1 Talimogene laherparepvec

Dose reductions – talimogene laherparepvec

Dose reductions with regards to changes in the concentrations of talimogene laherparepvec are not permitted. However, patients may require a reduction in the volume injected due to a disease response (defined in dosing section) or due to local toxicity at the injection site.

Dose delays and rules for withholding/restarting treatment – talimogene laherparepvec

If a subject experiences any of the following treatment-related toxicities, talimogene laherparepvec administration should be delayed until the toxicity has resolved to at least CTCAE grade 1 or baseline:

- grade 2 or greater immune-mediated adverse events, with the exception of vitiligo
- grade 2 or greater allergic reactions
- any other grade 3 or greater hematologic or non-hematologic toxicity

Upon restarting study therapy, the patient's treatment schedule should be reset from the date that therapy is reinitiated as to maintain appropriate treatment windows between therapy administrations.

If the subject requires corticosteroid dosing of >10 mg prednisone daily (or equivalent) and/or other immunosuppressive medication for related toxicities talimogene laherparepvec dosing must be held until the corticosteroid dose has decreased to ≤10 mg prednisone daily (or equivalent) and the administration of the other immunosuppressive medication has discontinued.

Subjects who are receiving talimogene laherparepvec may not receive systemic intravenous or oral antiherpetic drugs (e.g., acyclovir, valacyclovir, famciclovir), but may receive a topically administered antiherpetic drug more than 20 cm from a talimogene laherparepvec injection site. Dosing should be permanently discontinued if, in the opinion of the investigator, the subject develops clinical evidence of any systemic herpes infection (such as encephalitis or disseminated infection).

Dosing of talimogene laherparepvec could also be delayed for active herpetic cutaneous or mucosal lesions, herpes labialis, antiviral therapy, or active dermatoses in the region of the injected tumors.

Permanent discontinuation – talimogene laherparepvec

If talimogene laherparepvec dosing is delayed by more than 9 weeks from the last dose (approximately 12 weeks from the previous dose) due to the occurrence of adverse events that are related to talimogene laherparepvec, then treatment should be discontinued. If talimogene laherparepvec dosing is delayed by more than 9 weeks (approximately 12 weeks from the previous dose) for reasons other than treatment-related toxicity, the case must be reviewed by the principal investigator to determine if the subject can resume talimogene laherparepvec therapy.

Treatment with talimogene laherparepvec should be suspended if systemic intravenous or oral acyclovir or other anti-viral therapy is required; if ongoing treatment is required then treatment should be permanently discontinued.

In addition to criteria outlined in section 9.2, talimogene laherparepvec is to be permanently discontinued for subjects meeting any of the following criteria:

- A grade 2 or greater immune-mediated adverse event (with the exception of vitiligo) or allergic reactions attributed to talimogene laherparepvec that would require a dose delay of greater than 9 weeks from the date of the planned dose (i.e., approximately 12 weeks from the previous dose)

NOTE: immune-mediated glomerulonephritis, vasculitis, and pneumonitis and exacerbation of psoriasis have been observed in subjects receiving talimogene laherparepvec in clinical trials. Most of these subjects had a history of other autoimmune disease and/or prior treatment with agents that offered plausible

alternative etiologies; however, immune-mediated adverse events can potentially involve any organ system.

- Plasmacytoma has been observed with the administration of talimogene laherparepvec. Permanently discontinue talimogene laherparepvec if development of a plasmacytoma is observed.
- Any talimogene laherparepvec-related non-hematologic or hematologic toxicities Grade 3 or greater that, in the opinion of the investigator, would require a dose delay of greater than 9 weeks (approximately 12 weeks from the previous dose) or discontinuation of therapy.
- A female subject becomes pregnant or fails to use 2 highly effective methods of contraception (for those subjects who are able to conceive).
- A female subject breast feeds while on study treatment.
- The subject develops clinical evidence of any systemic herpes infection (such as encephalitis or disseminated infection).
- In the event talimogene laherparepvec is delayed or permanently discontinued for talimogene laherparepvec-related toxicity, pembrolizumab may continue to be administered, as long as the toxicity is clearly not related to pembrolizumab. Likewise in the event pembrolizumab is delayed or permanently discontinued for pembrolizumab-related toxicity, talimogene laherparepvec may continue to be administered, as long as the toxicity is clearly not related to talimogene laherparepvec.

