Note: Seasonal influenza vaccines for injection are generally inactivated flu vaccines and are allowed; however intranasal influenza vaccines (e.g., Flu-Mist®) are live attenuated vaccines, and are not allowed.
- Has a known history of active TB (Bacillus Tuberculosis)
- Female subject is pregnant or breast-feeding, or planning to become pregnant or male subject is planning to father a child within the projected duration of the trial, starting with the pre-screening or screening visit, during study treatment and through 3 months after the last dose of talimogene laherparepvec or 4 months after the last dose of pembrolizumab, whichever is later.
- Male and female subjects of childbearing potential who are unwilling to use acceptable method(s) of effective contraception during study treatment and through 3 months after the last dose of talimogene laherparepvec and 4 months after the last dose of pembrolizumab. (Note: Women not of childbearing potential are defined as: Any female who is post-menopausal [age \geq 55 years with cessation of menses for 12 or more months or less than 55 years but not spontaneous menses for at least 2 years or less than 55 years and spontaneous menses within the past 1 year, but currently amenorrhoeic (e.g., spontaneous or secondary to hysterectomy), and with postmenopausal gonadotropin levels (luteinizing hormone and follicle-stimulating hormone levels > 40 IU/L) or postmenopausal estradiol levels (< 5 ng/dL) or according to the definition of "postmenopausal range" for the laboratory involved] or who have had a hysterectomy, bilateral salpingectomy, or bilateral oophorectomy).
- Sexually active subjects and their partners unwilling to use male or female latex condom or polyurethane condoms for patients with latex allergies to avoid potential viral transmission during sexual contact while on treatment and within 30 days after treatment with talimogene laherparepvec.
- Subject who is unwilling to minimize exposure with his/her blood or other body fluids

to individuals who are at higher risks for HSV-1 induced complications such as immunosuppressed individuals, individuals known to have HIV infection, pregnant women, or children under the age of 1 year, during talimogene laherparepvec treatment and through 30 days after the last dose of talimogene laherparepvec.

- Known previous history of sensitivity to talimogene laherparepvec or any of its components to be administered during dosing (e.g. sorbitol, myo-inositol)

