11.7 Pregnancy Testing, Prevention and Lactation Reporting

11.7.1 Pregnancy Testing and Prevention

Talimogene laherparepvec is not considered to be teratogenic. Pembrolizumab may have adverse effects on a fetus in utero. Furthermore, it is not known if pembrolizumab has transient adverse effects on the composition of sperm.

For this trial, male subjects will be considered to be of non-reproductive potential if they have azoospermia (whether due to having had a vasectomy or due to an underlying medical condition).

The need for a screening pregnancy test depends on whether a female subject is of childbearing potential or non-childbearing potential.

Female subjects will be considered of non-reproductive potential if they are either:

(1) Postmenopausal (defined as at least 12 months with no menses without an alternative medical cause; in women < 45 years of age a high follicle stimulating hormone (FSH) level in the postmenopausal range may be used to confirm a post-menopausal state in women not using hormonal contraception or hormonal replacement therapy. In the absence of 12 months of amenorrhea, a single FSH measurement is insufficient.);

OR

(2) Have had a hysterectomy and/or bilateral oophorectomy, bilateral salpingectomy or bilateral tubal ligation/occlusion, at least 6 weeks prior to screening;

OR

(3) Has a congenital or acquired condition that prevents childbearing.

A female of child-bearing potential is defined as any female who does not meet the criteria of non-childbearing potential as described in the previous paragraph.

If a female subject is of childbearing potential, she must have a serum β -HCG pregnancy test at screening and performed within 72 hours of the first dose of study treatment. Subjects with positive pregnancy test result must be excluded from the study.

Female and male subjects of reproductive potential must agree to avoid becoming pregnant or impregnating a partner, respectively, while receiving study drug and for 90 days after the last dose of talimogene laherparepvec and 120 days after the last dose of pembrolizumab by complying with one of the following:

(1) Practice abstinence[†] from sexual activity;

OR

(2) Use (or have their partner use) acceptable contraception during sexual activity.

Acceptable methods of contraception during study treatment and up to 30 days following the final dose of talimogene laherparepvec include:

Male and female latex condoms

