Acceptable methods of contraception during study treatment from 30 days after the final dose of talimogene laherparepvec include:

Single method (one of the following is acceptable):

- intrauterine device (IUD)
- vasectomy of a female subject's male partner
- contraceptive rod implanted into the skin

Combination method (requires use of two of the following):

- diaphragm with spermicide (cannot be used in conjunction with cervical cap/spermicide)
- cervical cap with spermicide (nulliparous women only)
- contraceptive sponge (nulliparous women only)
- male condom or female condom (cannot be used together)
- hormonal contraceptive: oral contraceptive pill (estrogen/progestin pill or progestin-only pill), contraceptive skin patch, vaginal contraceptive ring, or subcutaneous contraceptive injection
- Abstinence (relative to heterosexual activity) can be used as the sole method of contraception if it is consistently employed as the subject's preferred and usual lifestyle and if considered acceptable by local regulatory agencies and ERCs/IRBs. Periodic abstinence (e.g., calendar, ovulation, sympto-thermal, post-ovulation methods, etc.) and withdrawal are not acceptable methods of contraception.
- If a contraceptive method listed above is restricted by local regulations/guidelines, then it does not qualify as an acceptable method of contraception for subjects participating at sites in this country/region.

Subjects should be informed that taking the study medication may involve unknown risks to the fetus (unborn baby) if pregnancy were to occur during the study. In order to participate in the study subjects of childbearing potential must adhere to the contraception requirement (described above) from the day of study medication initiation (or 14 days prior to the initiation of study medication for oral contraception) throughout the study period up to 120

days after the last dose of trial therapy. If there is any question that a subject of childbearing potential will not reliably comply with the requirements for contraception, that subject should not be entered into the study.

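### Section 11.4.1 permanently stops T-VEC unless two highly effective contraceptive methods are used, while 11.7.1 accepts abstinence or condoms alone during T-VEC; separately, 6.2 and 11.7.1 define childbearing potential differently

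*Combined protocol and SAP*

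**What the plan says.** **Stopping rule.** Section 11.4.1 lists criteria on which T-VEC has to be stopped for good. One of them reads "A female subject becomes pregnant or fails to use 2 highly effective methods of contraception", followed by a parenthesis that limits it to subjects able to conceive. Neither *highly effective* nor *able to conceive* is defined.

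**Contraception requirement.** Section 11.7.1 covers the time on study drug and the 90 days after T-VEC and 120 days after pembrolizumab. It offers two options. The first is abstinence. The second is "2) Use (or have their partner use) acceptable contraception during sexual activity". It adds that "Abstinence (relative to heterosexual activity) can be used as the sole method of contraception", on condition that this is the subject's usual and consistent practice and is acceptable to local regulators and review boards. Methods are then split by time:

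- Under the heading "Acceptable methods of contraception during study treatment and up to 30 days following the final dose of talimogene laherparepvec include" the only entry is latex condoms, of the male and female types.
- A second list starts 30 days after the last T-VEC dose. It has a part headed "Single method (one of the following is acceptable" (intrauterine device, partner's vasectomy, implanted rod) and a part with methods to be used in pairs. It also says that a male and a female condom may not be used at once.

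Section 6.2 excludes subjects unwilling to use acceptable contraception and leaves the number of methods open.

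**Childbearing potential.** Section 6.2 uses an age cut at 55. At or above it, 12 months without menses suffices. Below it the text asks for "less than 55 years but not spontaneous menses for at least 2 years", or for current amenorrhea with hormone levels in the postmenopausal range. Hysterectomy, bilateral salpingectomy and bilateral oophorectomy also count. Section 11.7.1 has no cut at 55. Its first criterion is "Postmenopausal (defined as at least 12 months with no menses without an alternative medical cause", and it says that one FSH value is not enough before 12 months have passed. It also counts tubal ligation or occlusion, requires surgery to be at least 6 weeks before screening, and accepts congenital or acquired conditions.

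**The concern.** A criterion for permanent withdrawal of a study drug should not be met by a patient who is doing what the protocol asks of her. Here the section that sets the contraception requirement and the section that enforces it use different standards, and neither refers to the other. Read literally, 11.4.1 would take T-VEC away from a compliant woman.

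The two definitions raise a different problem. They decide who needs the pregnancy test in section 6.1 and Table 6 and who must use contraception, and section 11.7.1 itself says that pembrolizumab may have adverse effects on a fetus. If the same woman is classified one way under 6.2 and another way under 11.7.1, staff cannot tell from the text which duties apply to her.

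**Working it through.** No arithmetic applies. The check sets the sections side by side and works through cases.

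**Step 1: contraceptive methods, for a woman able to conceive**

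| Case | Section 11.7.1 | Section 11.4.1 |
|---|---|---|
| On T-VEC, abstinent under the stated conditions | Complies: first of the two options | Fewer than two methods: criterion met |
| On T-VEC, condoms alone | Complies: the only listed method | One method: criterion met |
| On T-VEC, condoms plus a second method | No conflict shown | Depends on the undefined term *highly effective* |
| One single method, from 30 days after the last T-VEC dose | Complies | Ordinarily no T-VEC left to stop: not triggered |

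The sentence on abstinence as sole method is printed at the end of the later list. That does not weaken the first row, because the main requirement in 11.7.1 already offers abstinence for the whole time on study drug. For the second row, the T-VEC-period list contains condoms only and the two types may not be combined, so that list cannot by itself supply two simultaneous methods.

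**Step 2: childbearing potential**

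| Case | Section 6.2 | Section 11.7.1 |
|---|---|---|
| Age 50, 13 months without menses, no other medical cause, no hormone results | Of childbearing potential: 2 years not reached | Not of childbearing potential: 12 months reached |
| Tubal ligation only, at least 6 weeks before screening | Of childbearing potential: not listed | Not of childbearing potential |
| Age 50, amenorrhea under 12 months, qualifying hormone levels, no surgery or other condition | Can be not of childbearing potential | Of childbearing potential: 12 months not reached, and one FSH value does not replace them |

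In the first two cases 6.2 is the stricter section. In the third 11.7.1 is. Neither definition therefore contains the other, and reading the stricter one throughout does not settle which section is meant.

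**Step 3: link between the two.** The rule in 11.4.1 depends on *able to conceive*, not on either definition. The definitions leave it unclear who is covered by the rule. They do not themselves put a compliant woman in breach; the mismatch in Step 1 does that.

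**Step 4: effect on the toxicity boundary.** Section 11.1.1 counts a discontinuation as a treatment-related toxicity event only if the investigator judges it related to a study drug. A stop for contraception alone is not, so the boundary of 2/4, 3/8, 4/14 or 5/20 in section 14.1 is unaffected.

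**The case against.** The strongest reply is practical. This is a single-center trial, eligibility is confirmed on a signed checklist, and an investigator would probably read 11.4.1 as meaning failure to follow the contraception requirement. No patient is shown to have been affected. Section 16.3, in its text on data sharing, also describes the study as completed, so an amendment may have little prospective value. All of this limits the likely consequence. It does not remove the contradiction, because the criterion in 11.4.1 is mandatory as worded.

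Several stronger readings are tempting, and the documents do not support them:

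- *Women using one method such as an intrauterine device are also caught.* That list begins 30 days after the last T-VEC dose, when there is ordinarily no T-VEC to discontinue.
- *Every woman able to conceive is affected.* Only reliance on abstinence or condoms alone is shown to conflict.
- *The condom entry contradicts itself.* It reads as a list of acceptable types, which is consistent with the ban on using both at once and with the either-or wording in 6.2.
- *Sites would diverge.* Patients are treated at one center; the named participating sites do imaging or data analysis.
- *A looser definition lets women skip contraception or testing.* The exclusion criteria in 6.2 still bind at entry, and the test is required by 6.1. What is shown is ambiguity, not a waiver. Nor is every woman under 55 with 12 to 24 months of amenorrhea classified differently, since 11.7.1 requires that there be no other medical cause.
- *The response rate is distorted.* Section 11.4.1 addresses continuing pembrolizumab only when T-VEC stops for toxicity, section 13.0 allows some early departures to be replaced, and no affected patient is identified.

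**Conclusion.** The text is wrong as written, in a narrow form. During T-VEC, a woman able to conceive who relies on abstinence or condoms alone complies with 11.7.1 and literally meets a permanent stopping criterion in 11.4.1. As a separate matter, 6.2 and 11.7.1 define childbearing potential incompatibly, and 11.4.1 adds a third, undefined term.

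The conclusion rests on a literal reading of 11.4.1 and on the time windows in 11.7.1 as printed. The size cannot be given: the documents do not state how many enrolled women are able to conceive, which methods they use, or how many fall between the two definitions. The matter concerns protocol consistency and patient safety, with no demonstrated effect on an analysis.

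**What to change.** Reconcile sections 6.2, 11.4.1 and 11.7.1 so that one contraception requirement governs entry, treatment and T-VEC discontinuation. This can be done by having the criterion in 11.4.1 refer to the requirement in 11.7.1, or by restating 11.7.1 to match 11.4.1. Keep one definition of childbearing potential, cross-refer to it from 6.1, 6.2, 11.7.1 and the pregnancy-test note to Table 6, and use the same term in 11.4.1. The sponsor's medical and safety leads decide which standard and which definition apply; this review takes no position.

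The cost is amendment wording, plus a change to the consent form if the required methods change. No visits are added. Depending on the definition chosen, some women whom one section now treats as not of childbearing potential would need pregnancy testing.

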11.4.2 Pembrolizumab

Dose reductions – Pembrolizumab

Dose reductions of pembrolizumab are not permitted.

Dose Modification and Toxicity Management

Adverse events (both non-serious and serious) associated with pembrolizumab exposure, including coadministration with additional compounds, may represent an immunologic etiology. These adverse events may occur shortly after the first dose or several months after the last dose of pembrolizumab/combination treatment and may affect more than one body system simultaneously. Pembrolizumab must be withheld for drug-related toxicities and severe or life-threatening AEs as per table 10 below. See Section 5.6 for supportive care guidelines, including use of corticosteroids.

Attribution of Toxicity:

When study interventions are administered in combination, attribution of an adverse event to a single component is likely to be difficult. Therefore, while the investigator may attribute

a toxicity event to the combination, to talimogene laherparepvec alone or to pembrolizumab alone], for adverse events listed in Table 10, both interventions must be held according to the criteria in Table 10 Dose Modification and Toxicity Management Guidelines for Immune-Related Adverse Events Associated with Pembrolizumab.

Holding Study Interventions:

When study interventions are administered in combination, if the AE is considered immune-related, both interventions should be held according to recommended dose modifications.

Restarting Study Interventions:

Participants may not have any dose modifications (no change in dose or schedule) of pembrolizumab in this study, as described in Table 10.

- If the toxicity does not resolve or the criteria for resuming treatment are not met, the participant must be discontinued from all study interventions.
- If the toxicities do resolve and conditions are aligned with what is defined in Table 10, the combination of talimogene laherparepvec and pembrolizumab may be restarted at the discretion of the investigator.[In these cases where the toxicity is attributed to the combination or to talimogene laherparepvec alone, re-initiation of pembrolizumab as a monotherapy may be considered at the principal investigator's discretion

Table 10. Dose modification and toxicity management guidelines for immune-related AEs associated with pembrolizumab monotherapy and IO combinations

General instructions:				
Immune-related AEs	Toxicity grade or conditions (CTCAEv4.0)	Action taken to pembrolizumab	irAE management with corticosteroid and/or other therapies	Monitor and follow-up
Pneumonitis	Grade 2	Withhold	
• Administer corticosteroids (initial dose of 1-2mg/kg prednisone or equivalent) followed by taper• Add prophylactic antibiotics for opportunistic infections	
• Monitor subjects for signs and symptoms of pneumonitis• Evaluate subjects with suspected pneumonitis with radiographic imaging and initiate corticosteroid treatment
	Grade 3 or 4, or recurrent grade 2	Permanently discontinue		
Diarrhea / colitis	Grade 2 or 3	Withhold	
• Administer corticosteroids (initial dose of 1-2mg/kg prednisone or equivalent) followed by taper	
• Monitor subjects for signs and symptoms of enterocolitis (i.e. diarrhea, abdominal pain, blood or mucus in stool with or without fever) and of bowel perforation (i.e. peritoneal signs and ileus).• Subjects with ≥ Grade 2 diarrhea suspecting colitis should consider GI consultation and performing endoscopy to rule out colitis.

	Recurrent Grade 3 or Grade 4	Permanently discontinue		
 Subjects with diarrhea/colitis should be advised to drink liberal quantities of clear fluids. If sufficient oral fluid intake is not feasible, fluid and electrolytes should be substituted via IV infusion.
AST / ALT elevation or Increased Bilirubin	Grade 2 ^a	Withhold	
 Administer corticosteroids (initial dose of 0.5-1mg/kg prednisone or equivalent) followed by taper 	
 Monitor with liver function tests (consider weekly or more frequently until liver enzyme value returned to baseline or is stable)
	Grade 3 ^b or 4 ^c	Permanently discontinue	
 Administer corticosteroids (initial dose of 1-2mg/kg prednisone or equivalent) followed by taper 	
Type 1 diabetes mellitus (T1DM) or Hyperglycemia	Newly onset T1DM or Grade 3 or 4 hyperglycemia associated with evidence of β -cell failure	Withhold ^d	
 Initiate insulin replacement therapy for subjects with T1DM Administer anti-hyperglycemic in subjects with hyperglycemia 	
 Monitor subjects for hyperglycemia or other signs and symptoms of diabetes.
Hypophysitis	Grade 2	Withhold	
 Administer corticosteroids and initiate hormonal replacements as clinically indicated. 	
 Monitor for signs and symptoms of hypophysitis (including hypopituitarism and adrenal insufficiency)
	Grade 3 or 4	Withhold or permanently discontinue ^d		
Hyperthyroidism	Grade 2	Continue	
 Treat with non-selective beta-blockers (e.g. propranolol) or thionamides as appropriate 	
 Monitor for signs and symptoms of thyroid disorders.
	Grade 3 or 4	Withhold or Permanently discontinue ^d		
Hypothyroidism	Grade 2-4	Continue	
 Initiate thyroid replacement hormones (e.g. levothyroxine or liothyronine) per standard of care 	
 Monitor for signs and symptoms of thyroid disorders.
Nephritis: grading according to increased creatinine or acute kidney injury	Grade 2	Withhold	
 Administer corticosteroids (prednisone 1- to 2mg/kg or equivalent) followed by taper. 	
 Monitor changes of renal function
	Grade 3 or 4	Permanently discontinue		
Neurological Toxicities	Grade 2	Withhold	
 Based on severity of AE administer corticosteroids 	
 Ensure adequate evaluation to confirm etiology and/or exclude other causes
	Grade 3 or 4	Permanently discontinue		
Myocarditis	Grade 1	Withhold		
 Ensure adequate evaluation to confirm etiology and/or exclude other causes

	Grade 2, 3, or 4	Permanently discontinue	
 Based on severity of AE administer corticosteroids 	
Exfoliative Dermatologic Conditions	Suspected SJS, TEN, or DRESS	Withhold	
 Based on severity of AE administer corticosteroids 	
 Ensure adequate evaluation to confirm etiology or exclude other causes
	Confirmed SJS, TEN, or DRESS	Permanently discontinue		
All Other immune-related AEs	Grade 3, or intolerable/persistent Grade 2	Withhold	
 Based on severity of AE administer corticosteroids 	
 Ensure adequate evaluation to confirm etiology or exclude other causes
	Grade 4 or recurrent Grade 3	Permanently discontinue		

NOTES:

AE(s)=adverse event(s); ALT= alanine aminotransferase; AST=aspartate aminotransferase; CTCAE=Common Terminology Criteria for Adverse Events; DRESS=Drug Rash with Eosinophilia and Systemic Symptom; GI=gastrointestinal; IO=immuno-oncology; ir=immune related; IV=intravenous; SJS=Stevens-Johnson Syndrome; T1DM=type 1 diabetes mellitus; TEN=Toxic Epidermal Necrolysis; ULN=upper limit of normal.

Note: Non-irAE will be managed as appropriate, following clinical practice recommendations.

^a AST/ALT: >3.0 to 5.0 x ULN if baseline normal; >3.0 to 5.0 x baseline, if baseline abnormal; bilirubin:>1.5 to 3.0 x ULN if baseline normal; >1.5 to 3.0 x baseline if baseline abnormal
^b AST/ALT: >5.0 to 20.0 x ULN, if baseline normal; >5.0 to 20.0 x baseline, if baseline abnormal; bilirubin:>3.0 to 10.0 x ULN if baseline normal; >3.0 to 10.0 x baseline if baseline abnormal
^c AST/ALT: >20.0 x ULN, if baseline normal; >20.0 x baseline, if baseline abnormal; bilirubin: >10.0 x ULN if baseline normal; >10.0 x baseline if baseline abnormal
^d The decision to withhold or permanently discontinue pembrolizumab is at the discretion of the investigator or treating physician. If control achieved or ≤ Grade 2, pembrolizumab may be resumed.
^e Events that require discontinuation include, but are not limited to: encephalitis and other clinically important irAEs (eg, vasculitis and sclerosing cholangitis).

Dosing interruptions are permitted in the case of medical / surgical events or logistical reasons not related to study therapy (e.g., elective surgery, unrelated medical events, patient vacation, and/or holidays). Subjects should be placed back on study therapy within 3 weeks of the scheduled interruption, unless otherwise discussed with the principal investigator. The reason for interruption should be documented in the patient's study record. The patient's treatment schedule should be reset from the date that therapy is reinitiated.

